Solriamfetol is a dopamine and norepinephrine reuptake inhibitor that the FDA has approved for treatment of excessive daytime sleepiness in patients with narcolepsy or obstructive sleep apnea²². It is a class IV controlled substance, and clinical trials suggest it is well tolerated. Conventional therapies for ADHD, including the stimulants methylphenidate and mixed amphetamine salts, and the nonstimulant atomoxetine, are thought to work in part through reuptake blockade and/or increased release of the catecholamines dopamine and norepinephrine. ¹³ Prior studies with modafinil and bupropion and mazindol also suggest ADHD benefit from these agents with dopamine and norepinephrine reuptake properties. Solriamfetol is thought to support dopamine and/or norepinephrine activity.

Prior clinical data to support efficacy in sleep disorder indications, and the product's well-elaborated safety profile, also suggest potential favorable application for ADHD care. Other agents approved by the FDA for ADHD are closely controlled substances (stimulant agents) or may take longer to work than first-line stimulants or have less effect than stimulants (e.g. atomoxetine and

guanfacine). If Solriamfetol had moderate effect size for ADHD symptoms, it may open up an option for a new method of treating ADHD.

Because Solriamfetol could have positive effects on ADHD symptoms, has not been evaluated in ADHD, and is expected to be and well tolerated, we propose to conduct a double-blind pilot study enrolling 60 adults with ADHD. Such a pilot study can determine whether Solriamfetol is likely to have a moderate effect size for this indication. Using a dose-optimization protocol, we will maximize ability to estimate clinical effects. To assess the safety and efficacy of Solriamfetol, we will use ratings of spontaneously reported adverse events and ADHD symptoms as primary outcome measures. Adults with moderate levels of ADHD will be enrolled. We choose to evaluate response over six weeks, as this has been a typical format sensitive to mild to moderate effects on ADHD, allows for dose titration, and sufficient exposure durations for participants to notice and evaluate a clinically useful effect.

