Just as telemedicine has expanded the scope of clinical care, it is also expanding the scope of clinical trials²³. The outpatient psychiatry clinics at Massachusetts General Hospital have used telemedicine for routine clinic appointments for qualifying patients after an in-person consultation. Telemedicine significantly lessens patient burden, as the patient does not have to come into the office for appointments, but still receives the same level of clinical care through the face-to-face video conference. Our research unit has conducted telemedicine research with positive experiences. As such, we propose to offer the option of telemedicine visits in this study.

II. SPECIFIC AIMS

Aim 1: Assess effect of solriamfetol on ADHD symptoms and associated ADHD features.

Hypothesis 1: Compared to pre-administration baseline, solriamfetol will be associated with a greater reduction than placebo of ADHD symptoms (1a). We also expect drug exposure to be correlated with a greater rate of individuals achieving an a priori definition of clinical improvement, with at least a 25% reduction in ADHD symptoms, and a CGI of much or very much improved (1b).

We secondarily will explore whether there are reduced symptoms of executive dysfunction (defined by a 0.5 standard deviation improvement on the Brief Rating Inventory of Executive Function-Adult Version (BRIEF-A) self-report total or subscale scores). We also will explore whether baseline ratings of sleepiness, or deficits on BRIEF predict improvements on the Adult ADHD Investigator Symptom Rating Scale (AISRS) or BRIEF measures.

Aim 2: Assess the safety of solriamfetol in the treatment of ADHD among adults

Hypothesis 2: Solriamfetol will be well tolerated by adults with ADHD.

III. SUBJECT SELECTION

We plan to enroll 60 subjects of any gender identity between the ages of 18-65 in the study. No pediatric subjects will be recruited for this study. We will recruit subjects through advertisement in the general community, using flyer and internet advertisements, via postings on Rally, Research Match, and from the referral pool of patients of the Clinical and Research Program in Pediatric Psychopharmacology and Adult ADHD at Massachusetts General Hospital. As noted elsewhere, however, the informed consent process with a subject must occur with a different clinician than one they have seen as a treating provider.

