Individuals who express interest in the study will be screened for eligibility by the study coordinator or a research assistant via phone. A phone script will be used that is IRB-approved. If they meet criteria, the participant will be asked to complete study scales online via RedCap, a secure

online data capture system. These self-report scales will include the ADHD Rating Scale (ADHD-RS), Adult Self-Report Form (ASR), BRIEF-A, Epworth Sleepiness Scale (ESS), and the Pittsburgh Sleep Quality Index (PSQI). If a subject completed any of these scales for another study in our department or through the adult ADHD clinical program within the past year prior to screening they may not have to repeat the scale(s) for the current study unless asked to do so by a study staff member based upon clinician judgment. However, in the case where scales completed previously will be reviewed, verbal permission will be obtained from the participant that it is okay to review these previously completed scales to assess inclusion and exclusion criteria.

Subjects who have participated in research in our program may be eligible to participate in this study. Other medical records on a subject will not be used at any point, unless explicit written permission is provided by the subject.

Many subjects referred to this study will first participate in our general screening protocol entitled, "Screening Protocol for Adults with Attention Deficit Hyperactivity Disorder" (Protocol # 2002-P-001856). Under this protocol, advertisements from our research group include a link that allows individuals to contact us by email, phone, or via a URL link to a REDCap form. After participating in this screening protocol, subjects are referred to specific studies based upon eligibility requirements (i.e. age, prior medication efficacy or tolerability).

Study Entry Criteria

Inclusion Criteria:

- 1. Adults ages 18-65 years of age.
- A diagnosis of childhood-onset ADHD, meeting the DSM-V criteria for ADHD in adulthood, including at least 5 current symptoms of inattentive or impulsive-hyperactive traits, and childhood onset by age 12, defined as two symptoms of inattentive or of impulsive/hyperactive traits by the age of 12.
- 3. A score of 20 or more on the Adult ADHD Investigator Symptom Report Scale (AISRS)

Exclusions

- 1. Individuals with known renal insufficiency or renal impairment.
- 2. A history of intolerance to solriamfetol

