Females who are able to have children will also have a urine pregnancy test at evaluation, and week 6 or study completion. If a participant has a positive pregnancy test she will not be able to take part in the study. As detailed in the exclusion criteria, all participants will be required to use contraception adequate to avoid conception, or to not participate. In the event that a subject becomes pregnant, we will ask the subject's permission to obtain information about the outcome of the pregnancy and the condition of the newborn. In the event that a subject reports contributing sperm to a pregnancy during the study period, we will also ask the subject's permission to obtain information about the outcome of the pregnancy and the condition of the newborn. Those subjects who terminate study participation before the completion of the study will be asked to complete all tasks scheduled to take place on the final study visit at the time of study discontinuation.

We will increase our chances of identifying exclusionary mental health conditions by supplementing the clinical interview for study eligibility with review of self-report on the Adult Self-Report (ASR), a self-report scale validated to identify major mental health conditions, prior to participation.

Subject Dosing and Visit schedule:

Visits will occur for evaluation, baseline, and weekly for weeks 1, 2, 3, 4, 5 and 6. Visits will be conducted at 7 day intervals, +/- 3 days. Doses will be assigned at each study visit for the period of time until the next visit, with forced-dose up-titration as tolerated from 75 mg at week one to 150 mg at week 2, and with intention that dosing remain stable for the last four weeks of study participation, such that investigators will ask a subject to go back down to 75 mg during any of the weeks following week 2 only if only if 150 mg is not tolerated. Thus, the most robust titration would be 75 mg until week 1, and 150 mg for the rest of study. The least robust titration where a subject maintains participation would be 75 mg for the duration of the study.

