Randomization to active or placebo will occur once a subject is scheduled for a baseline visit, when the clinical trials pharmacy will be given a subject name that the pharmacy will associate with a number identifier. We have extensive experience maintaining blinding, wherein we have our central Mass General Hospital Clinical Trials Pharmacy pharmacy serve as the only part of the greater trial team that is aware of the assignment to active or placebo during study participation. The trials pharmacy will receive products identified by the sponsor as active or placebo fill, over-encapsulate these products to look identical, bottle these products with unique identifiers, maintains the placeboactive ratio, and maintain blinding until study completion. For the purpose of the final analysis, the official clinical database will not be unblinded until medical/scientific review has been completed, protocol violators have been identified (if appropriate), and data collection has been declared complete. In the extreme event where subject safety will be compromised by maintaining the blind, eg. an adverse event where treatment is dependent on knowing if they were on active or placebo medication, we will unblind the status of the subject's study agent, following emergency protocols in place in our department and institution.

Assessments and Instruments:

Our primary endpoint will be change in the Adult ADHD Investigator Symptom Rating Scale (AISRS), the instrument we will use to evaluate ADHD symptom burden. We also will evaluate spontaneously reported adverse events as our main outcome of tolerability. At screening evaluation, AISRS ratings and concurrent medication treatments will be recorded. In addition, at screening or baseline, a brief demographic interview will be conducted to obtain information used to calculate socioeconomic status.

Demographic information, including socioeconomic status data, will collected for each participant.²⁴

During the study, the following assessments and instruments will be used:

Clinician rated assessments (rated at each in-office study visit, unless otherwise noted):

- Global Assessment of Functioning (GAF) scale. The GAF will assess global functioning using a scale from 1 (worst) to 100 (best). This will be collected at all study visits, excluding the screening visit.
- Clinical Global Impressions (CGI) scale for ADHD. The CGI is a measure of illness severity, improvement, and efficacy of treatment.

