If clinically appropriate, any subjects taking medication exclusionary to the study must be tapered off this medication prior to baseline visit for the length of 5 half-lives of the medication, corresponding to 95% of the agent leaving the participant's system), plus several days to assess the participant off medication. Individuals may participate if they prefer not to take a previously optimized treatment for documentable reasons such as side effects, perceived risks, personal preference, or lack of sufficient benefit. However, subjects will not enter the study if it would require tapering or otherwise stopping a medication that is optimally and comfortably managing a clinical concern likely to cause unaccommodated suffering of the participant. For example, a participant may prefer to participate in the trial after stopping a stimulant treatment that causes side effects but helps them in school, during a summer vacation period where the consequences of stopping and participating will be accommodated by lack of school participation and more time to complete daily tasks. Medication tapers will be monitored by the study clinician in agreement with the research subject and in consultation with the prescribing physician. No subject will be removed from a stable and effective treatment regimen for the purposes of participating in the study.

Subjects will be instructed not to take any medications or supplements that are contraindicated by exclusion criteria for the study. All new medications and supplements started during the study will be reviewed by the PI, and subjects may be dropped from study participation, but their data will be retained in the safety and intent-to-treat analyses with PI discretion.

In addition, any subject found to be taking medication listed as exclusionary during the course of the study or the seven days prior to randomization will be evaluated by the PI for ongoing eligibility.

Study Discontinuation Criteria

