Examples of individuals who will discontinue study participation include those who: 1) develop intolerable adverse events (AEs) despite dose adjustments; 2) have (a) clinically relevant serious AE(s) as determined by the investigator; 3) have worsening ADHD symptoms (much worse or very much worse as rated on CGI-Improvement at two consecutive visits); or 4) have emergent adverse mental health state including psychosis, suicidality, substance use, or worsening mood and/or anxiety; 5) are non-adherent to study procedures or withdraw from the study; 6) intend to be or become pregnant.

If study participation is discontinued due to safety reasons, participants will receive two followup visits, giving adequate time for appropriate psychiatric referrals to treaters in their communities. Subjects found to be taking substances listed as exclusionary during the course of the study may be discontinued based on PI evaluation of their eligibility.

VI. BIOSTATISTICAL ANALYSIS

Data processing and management followed procedures developed by the investigators and used in ongoing studies. Up to 30 subjects will receive Solriamfetol, and up to 30 subjects will receive placebo. Changes in outcome ratings within and between study groups will be tested.

Hypothesis 1 will be our main testable hypothesis, tested by evaluating whether the group receiving stimulant treatment has a significantly greater improvement in ADHD symptom rating. We will also explore exploratory hypotheses. This will include comparing the active and placebo arms on: the rate of individuals achieving an a priori definition of clinical improvement, with at least a 25% reduction in ADHD symptoms, and a CGI of much or very much improved (1b), and the rate of reduced symptoms of executive dysfunction (defined by a 0.5 standard deviation improvement on BRIEF-A self-report total or subscale scores) (1c).

All other analyses will be exploratory and p-values will be reported as nominal, and not used to infer significance. We will also explore descriptively whether baseline sleep problems, sleepiness, or deficits in domains of the BRIEF predict improvement on AISRS or BRIEF ratings.

Our primary test of Hypothesis 2 will be review of the occurrence of moderate or severe adverse events, and description of reasons for study dropout. We will also report rates of the same adverse event in active and placebo arms occurring two or more times for a particular subject.

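### The primary AISRS comparison names no baseline covariate; committing to adjustment for Visit 0 AISRS would usually make it more precise at almost no cost

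*Combined protocol and SAP*

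**What the plan says.** Section V (Assessments and Instruments) sets the endpoint: "Our primary endpoint will be change in the Adult ADHD Investigator Symptom Rating Scale (AISRS". Section II (Specific Aims) frames Hypothesis 1a in the same terms: "Compared to pre-administration baseline, solriamfetol will be associated with a greater reduction than placebo of ADHD symptoms (1a". Section VI makes Hypothesis 1 the main test, "tested by evaluating whether the group receiving stimulant treatment has a significantly greater improvement in ADHD symptom rating", adds only that "Changes in outcome ratings within and between study groups will be tested", and treats the remaining p-values as nominal. Baseline sleep, sleepiness and BRIEF scores appear there as descriptive predictors, not as covariates in the primary test. Each arm has at most 30 participants.

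The timeline table schedules clinician-rated AISRS at evaluation, Visit 0 and every week to week 6 or drop-out. Section I says "We choose to evaluate response over six weeks", so week 6 is the natural analysis point, but no sentence about AISRS fixes it.

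On leavers, Section V (Safety Assessments) says that they "will be asked to complete all tasks scheduled to take place on the final study visit at the time of study discontinuation", and a footnote to the timeline agrees. Section V (Concomitant Medications / Treatments) says of participants dropped over new medications or supplements that "their data will be retained in the safety and intent-to-treat analyses with PI discretion". No general rule says how a leaver's rating enters the primary comparison.

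**The concern.** The sentences on the primary test use baseline only as the reference point for change. If the analysis follows them literally, it subtracts the whole baseline score from each week-6 score. That removes too much when baseline predicts the outcome only partly, and the excess goes into the standard error. Adjustment estimates how much of the baseline to remove.

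Precision matters here because Section I gives the trial's purpose as judging whether a moderate effect is likely, and this is the only test used for inference. With 30 per arm the interval is wide, mainly because of sample size. Using a measurement already scheduled is one of the few ways to narrow it without more participants or visits. A model chosen after unblinding would also leave open whether the choice depended on the result.

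**Working it through.** **Inputs from the documents.** Up to 30 per arm; AISRS at Visit 0 and weeks 1 to 6; entry requires "A score of 20 or more on the Adult ADHD Investigator Symptom Report Scale (AISRS". There is no power calculation to reproduce.

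**Assumed inputs.** Two-sided 5%; true difference 0.5 SD of change; correlation ρ between Visit 0 and week-6 AISRS of 0.3, 0.5 or 0.7; ratio k of baseline SD to week-6 SD of 1, 0.85 or 0.7. Week-6 SD is set to 1.

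**Unadjusted change, 30 per arm.** Standard error = √(2/30) = 0.258 SD of change. Half-width = t(58) × 0.258 = 2.002 × 0.258 = 0.517. Noncentral-t power = 0.478. Power of 80% would need 64 per arm.

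**Effect of adjustment.** The variance of change is 1 + k² − 2ρk. The variance after adjustment is 1 − ρ². The first minus the second is (k − ρ)², which is never negative. So in large samples adjustment cannot lose, and the two methods tie when k = ρ. Estimating the slope multiplies the adjusted variance by 1 + 1/(60 − 4) = 1.018. The ratio is therefore

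R = 1.018 × (1 − ρ²)/(1 + k² − 2ρk), with 57 degrees of freedom.

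Example, k = 1 and ρ = 0.5: R = 1.018 × 0.75/1.00 = 0.763; standard error = 0.258 × √0.763 = 0.226; half-width = 0.452; power = 0.587.

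| k | ρ | R | Power, 30/arm | Half-width, 30/arm (SD of change) | Power, 24/arm |
|---|---|---|---|---|---|
| 1 | 0.3 | 0.662 | 0.648 | 0.421 | 0.547 |
| 1 | 0.5 | 0.763 | 0.587 | 0.452 | 0.490 |
| 1 | 0.7 | 0.865 | 0.535 | 0.481 | 0.444 |
| 0.85 | 0.3 | 0.764 | 0.586 | 0.452 | 0.490 |
| 0.85 | 0.5 | 0.875 | 0.530 | 0.484 | 0.440 |
| 0.85 | 0.7 | 0.975 | 0.487 | 0.510 | 0.402 |
| 0.7 | 0.3 | 0.866 | 0.534 | 0.481 | 0.443 |
| 0.7 | 0.5 | 0.966 | 0.491 | 0.508 | 0.405 |
| 0.7 | 0.7 | 1.018 | 0.471 | 0.522 | 0.388 |
| Unadjusted | | 1 | 0.478 | 0.517 | 0.396 |

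R is for 30 per arm. The last column assumes that 20% of participants are lost under either method (slope factor 1 + 1/44 = 1.023, 45 degrees of freedom when adjusted). At both sample sizes adjustment gives higher power in 8 of the 9 cells.

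**Fixing the raw effect instead.** The table fixes the effect in SD of change, so the raw effect differs between rows. With a raw effect of 0.5 week-6 SD, unadjusted power is 36% to 76% and adjusted power 51% to 75%. The change ranges from −0.8 to +14.4 points.

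**Entry threshold.** A simulation with 30 per arm and entry cut at 20 (AISRS mean 32 and SD 10 before the cut, and a 5-point effect, all assumed) gave variance ratios of 0.78, 0.84 and 0.92 for ρ of 0.3, 0.5 and 0.7 before the cut. Power rose from 41% to 50%, 52% to 60% and 72% to 75%. The gain shrinks but remains.

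**Repeated measures.** With 20% non-informative dropout, a constant correlation of 0.5 treated as known, and a difference of 0.5 week-6 SD, approximate power was 41% for completers' change, 52% for completers' ANCOVA and 53% for a model of all weekly ratings. In that scenario the covariate supplies nearly all of the gain.

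**The case against.** The strongest objection is that the comparator is not in the plan. The documents name an endpoint and a direction but no test, and an endpoint of change is compatible with ANCOVA. With baseline as a covariate, modelling change or the week-6 score gives the same arm difference, because subtracting baseline from the outcome only lowers the baseline slope by 1. This stands. A reader might infer that the plan has chosen an inefficient or invalid analysis; the documents do not support that. What remains is that the plan does not commit to adjustment, and its literal wording describes an analysis without it.

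The inputs are also all assumed. The largest gain needs equal spread at baseline and week 6 with a correlation of only 0.3, and the entry threshold makes equal spread less likely. This stands too, and is why ranges are given.

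A reader might also infer that adjustment pays only if leavers are kept. That inference sets adjusted power at 24 per arm (39% to 55%) against unadjusted power at 30 per arm (48%), which measures lost participants, not adjustment. An unadjusted change test needs the same endpoint rating, so whatever loses leavers from one loses them from the other.

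Finally, a six-visit repeated-measures model might seem necessary. In the scenario above it adds about one point of power over ANCOVA, so it is an option and not the core change.

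**Conclusion.** The point holds as an efficiency recommendation, not as an error in the plan. On the assumed inputs, adjustment moves power from 48% to 47–65% and the half-width from 0.52 to 0.42–0.52 SD of change at 30 per arm. At 24 per arm under both methods, power is 40% unadjusted and 39–55% adjusted. The one losing cell (ρ = k = 0.7) costs about 2% in variance and under 1 power point. No cell reaches 80%, so adjustment does not make up for the sample size.

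How leavers are handled is a separate question, of bias and of which population is analysed. It belongs in the same paragraph of Section VI because the primary analysis is incomplete without it, and because discretion over whose data are retained should not bear on the only inferential test. The change is worth making; confidence is medium because the actual gain cannot be read from the documents.

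**What to change.** Before the database is unblinded, add to Section VI:

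- The primary analysis is the arm difference in week-6 AISRS (equivalently, in change to week 6) from a model with Visit 0 AISRS as covariate, reported with its 95% CI. Naming Visit 0 matters because AISRS is also rated at evaluation.
- One rule for leavers' drop-visit ratings, applied to every randomised and dosed participant, including those dropped over new medications or supplements, and not left to discretion.

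A repeated-measures model of weeks 1 to 6 with the same covariate is an acceptable alternative. It relies on data being missing at random. An unstructured covariance over six visits has 6 × 7/2 = 21 parameters for 60 participants, so a simpler fallback structure should be named. Placing a drop-visit rating at the week it occurred, instead of using it as the endpoint, changes what is estimated, so the text should say which is intended.

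The cost is a few sentences and a standard model on ratings already scheduled. The statistical downside is the small loss shown above when the correlation and the SD ratio are both about 0.7.
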